5.6 CRITERIA FOR WITHDRAWAL OF PATIENTS AND PROCEDURES TO FOLLOW

Patients can leave the study at any time, without having to give no explanation. Additionally, patients may be withdrawn from the study for the following reasons:

1. They have adverse events that affect participation in the study

2. They do not wish to continue (withdrawal of consent) for any reason.

3. Violation of protocol or significant deviation from specific procedures

of the study

4. Loss of follow-up

5. Appearance of a clinically significant intercurrent disease that affects the participation in the study.

6. The investigator considers that it is beneficial for the patient to withdraw from the study. The withdrawal of the patient from the study will not represent for him any type of damage in the control of their disease, in subsequent treatments or in the treatment to be received by the doctor. If a patient is withdrawn from the study at any time the reason must be recorded in the corresponding sheet of the data collection notebook (CRD). Patients who are withdrawn from the study due to an adverse event or abnormal results of laboratory values should be followed up to total trial resolution or for a period of time considered clinically reasonable by the researcher.

Patients withdrawn from the trial due to an adverse event will be included in security analysis. Patients who have undergone surgically intervened for graft insertion. If a patient is lost, an attempt should be made to contact him. The investigator it should reflect the loss of follow-up in the medical history.

The aim of the study is to obtain 12 evaluable patients in each trial arm (24 in total). A patient will be considered evaluable as long as it has been infiltrated into the space intervertebral a dose of MSV or belongs to the control group. In the event that for some cause the application cannot be made to an included patient, another must be included patient in the same group until reaching the 12 patients treated in each arm of the clinical trial. The study exit and the causes of the study exit of the initial patient and no further follow-up will be necessary since they will not have received the Trial treatment.

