ANNEX VIII: MODIC CHANGES
ANNEX IX: RESEARCHER SIGNATURES PAGES A25
ANNEX X: INSURANCE POLICY
ANNEX XI: INSURANCE CERTIFICATE (Art.8; RD223 / 2004) A27

1. SUMMARY

Type of request:

Phase I-II, single-center, prospective, randomized, blinded ** and controlled clinical trial for the treatment of lumbar degenerative disc disease with allogeneic mesenchymal cells (MSV *), with two arms with 12 patients each. In the experimental arm, cells will be administered locally in the nucleus pulposus area of the affected segment "Ex Vivo" expanded allogeneic mesenchymal cells with the IBGM GMP procedure (MSV; PEI No. 10-134; authorized by the AEMPS). The control arm will infiltrate the area of the paravertebral musculature close to the injury with saline solution containing mepivacaine at 1% in the same volume and subject to the same maneuvers as the intervention on the arm experimental.

** Double blind, masked for the patient and evaluators performing the analysis of the results, open to the doctor who applies the cells.

Data relating to the Sponsor:

Citospin, Scientific Park of the University of Valladolid R + D Building, [name] NIF: NIF. B-47673538 Title of the clinical trial: Treatment of lumbar degenerative disc disease with allogeneic mesenchymal cells (MSV *). * MSV = Mesenchymal cells of the bone marrow prepared by the procedure of IBGM of Valladolid.

Protocol Code: Disc_allo_MSV Eudra-CT: 2012-004444-30

Experimental and control drug: dose, pharmaceutical form, route of administration, therapeutic group:

Experimental drug: The investigational drug or product is MSV, which is Mesenchymal bone marrow stromal cells obtained from healthy donors with negative serology (NAT; nucleic acid technology) and processed according to procedure of the IBGM (PEI Num. 10-134; approved by AEMPS), with the following characteristics: \Box Cell dose: 25x10e6 ± 5x10e6 MSV per disk.

□ Presentation: 2 ml of cell suspension in Ringer-lactate isotonic with 0.5% human albumin and 5 mM glucose in a 5 ml syringe. Stability:> 12 hours at 4-20 °C

□ Administration: Injection into the nucleus pulposus area of the affected disc

□ Therapeutic Group: Cell Therapy

Control drug: Injection of 2 ml of 1% mepivacaine in saline serum (see section 2.4). in the paravertebral musculature close to the injury, using the same volume and the same maneuvers as the intervention in the experimental arm.

Cell Production

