Citospin, Cell Production Unit, Scientific Park of the University of Valladolid, R + D Building, [name]. [contact]. Technical Director: Dra. [name]

Phase of the clinical trial

Phase I-II

Objectives:

Main goal:

□ Evaluate the feasibility and safety of the local use of allogeneic MSV for the treatment of lumbar degenerative disc disease.

Secondary objectives:

□ Evaluate the efficacy of allogeneic MSV treatments using criteria of clinical evolution objectified by the low back pain questionnaires (Visual Scale Analog, VAS), disability (Oswestry questionnaire) and quality of life (questionnaire SF-36 in its abbreviated version, SF-12).

Follow-up of the evolution of disc dehydration by the images of MRI calibrated at T2.
Compare the efficacy of the treatments in the control and experimental arms.

Total number of patients

The number of patients treated will be 24, 12 for each of the branches.

Participating countries

The study will be carried out at the Hospital Clínico Universitario de Valladolid. [name], Spain

Treatment duration

The implantation will be carried out in a single session and the evolution of the patients for 12 months.

Schedule and expected completion date

Start of study: last quarter of 2012

Recruitment: for a maximum of 6 months, until 12 patients are obtained for each branch.

Duration of the trial: 12 months after the treatment of the last patient.

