5.8 FOLLOW-UP OF PATIENTS

The research team will inform all patients entering the study of the need to follow a specific periodic control and the importance of going to the planned visits.

To patients who experience adverse events (regardless of whether they have dropped out or withdrawn from the study) will be followed until the incidence has subsided. resolved or stabilized at a level acceptable to both the coordinator and the promoter of the study. As it is a single administration, the option of withdrawal of the medication so it is expected that these patients can continue the follow-up provided in the protocol. All patients included in the study who received cell therapy (including patients who have voluntarily left the study or are withdrawn from it) will continue regular check-ups after participation in the study. These controls will be carried out in the Orthopedic Surgery and Traumatology Service of the Hospital Clínico Universitario de Valladolid with a frequency not less than once a year. These controls should include a clinical evaluation, an X-ray and a general analysis (acceptable if they have been carried out up to 3 months before the visit). The follow-up will be done with a minimum of 5 years. In case that any relevant information was detected for the study related to both the efficacy of the product as well as the safety of the subject (and attributable to the therapy received) is will notify the promoter, initially by telephone and, if deemed appropriate, facilitating supporting documentation (signed report or adverse event form serious) by fax or email.

In addition, and as indicated in the next point, to all patients who have received medication in the study will be given a Participation Card. At this time The research team will ask them that, in case of presenting a health problem relevant inform the doctor who attends you about your participation in said trial clinician by presenting said card. Particular attention will be paid to possibility of histological study if at any time a surgical technique is practiced on the treated area. This follow-up is not required for control patients.

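### Section 5.6 allows treated patients to be withdrawn from the study after the single injection, and no text secures their V2–V5 assessments, so these data can be lost

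*Combined protocol and SAP*

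**What the plan says.** Section 5.6 names six reasons for which a patient may be withdrawn from the study. Item 3 is "Violation of protocol or significant deviation from specific procedures"; item 5 is a clinically significant intercurrent disease; item 6 reads "The investigator considers that it is beneficial for the patient to withdraw from the study". None is tied to a time before or after treatment.

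The Summary describes treatment as one event ("The implantation will be carried out in a single session") followed by 12 months of observation. Section 7.2 places the injection at V1 and the later visits at day 8 (V2) and at 3, 6 and 12 months (V3 to V5). VAS, Oswestry and SF-12 are due at V3 to V5, MRI at V4 and V5.

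Section 5.8 speaks of patients with adverse events and then, because there is only one administration, says "it is expected that these patients can continue the follow-up provided in the protocol". It also keeps cell recipients, including those who leave or are withdrawn, in check-ups at least once a year for at least 5 years: "These controls should include a clinical evaluation, an X-ray and a general analysis". Its last sentence releases control patients from this follow-up.

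On masking, the Summary says that the trial is "open to the doctor who applies the cells". Section 11.3.2 restricts the efficacy analysis to patients without major violations who have a final efficacy rating.

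**The concern.** With a one-off treatment, withdrawal from treatment after V1 has no meaning for the trial injection. Withdrawal from the study does: it ends the visits that supply the efficacy variables and the scheduled safety assessments. If the reason for removal is linked to how the patient is doing, or to knowledge of the arm, the remaining patients no longer give a fair comparison. Data that were never collected cannot be restored by a later choice of analysis set.

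Safety is the main objective and is touched as well. A control patient removed without an adverse event has no required follow-up, while a cell recipient in the same position still has yearly check-ups. Later events could then be recorded unequally in the two arms.

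**Working it through.** **1. Which text covers a treated patient withdrawn after V1?**

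| Reason in 5.6 | Do the V2–V5 assessments continue? | Source |
|---|---|---|
| Item 1, adverse event | Expected to continue | 5.8 |
| Item 3, deviation | Not stated | none |
| Item 5, intercurrent disease | Not stated, unless handled as an adverse event | none |
| Item 6, investigator's judgement | Not stated | none |

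**2. Do the yearly check-ups fill the gap?** In part, and in one arm only. For withdrawn cell recipients they include an X-ray, and disc height on X-ray is a listed criterion in 3.3.1. They do not name VAS, Oswestry, SF-12 or MRI, and they are not aligned with the 6-month visit. Controls have nothing equivalent.

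**3. Are removed patients replaced?** The replacement rule after the 5.6 list applies only when the application could not be made. A treated patient who is later removed is not replaced.

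**4. Size.** There is no planned figure to reproduce beyond 2 × 12 = 24. Sections 5.4 and 11.1 fix the sample without power, SD or dropout rate, so what follows is illustration.

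- Weight of one removal: 1/12 = 8.3% of an arm.
- Removing k of 12 shifts that arm's mean by (k/12) × (mean of those kept − mean of those removed). The shift in the comparison is this quantity in one arm minus the same quantity in the other, so similar removals in both arms largely cancel.
- Random removal, simulated with 200,000 runs, normal outcomes with SD 1, no true effect and a two-sided t-test at 0.05: taking 1, 2 or 3 of 12 from one arm gives no bias, and the type I error stays at 0.05.
- Worst-outcome-first removal from the cell arm only, same simulation:

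| Removed | Bias (SD) | Two-sided type I error |
|---|---|---|
| 1 | 0.15 | 0.075 |
| 2 | 0.27 | 0.114 |
| 3 | 0.39 | 0.166 |

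- Precision: the difference detectable with 80% power (noncentral t) is 1.20 SD with 12 v 12, 1.26 SD with 12 v 10 and 1.30 SD with 12 v 9.

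The worst-first rows are an upper bound, not a forecast. The documents give no withdrawal rate and no link between removal and outcome.

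**5. End of adverse-event follow-up.** For patients withdrawn because of an adverse event, 5.6 lets follow-up end after a time that the investigator finds clinically sensible. Section 5.8 requires resolution, or stabilisation that both the coordinator and the sponsor accept. These are different stopping points for the same patients.

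**The case against.** The strongest reply is that the protocol means to follow everyone it treats. Section 5.6 waives further follow-up for patients who could not be treated because they did not receive the trial treatment, which implies that treated patients are followed. The single-administration argument in 5.8 fits every patient. Both sections contain broken sentences, including one in 5.6 about treated patients that lacks its predicate, so a rule may have been lost in translation or PDF reading. This makes the intention plausible, but no readable text requires the V2–V5 assessments after withdrawal under items 3, 5 or 6.

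Several stronger readings are tempting and are not supported:

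- *Endpoints will be lost selectively.* Section 5.6 says only that patients may be withdrawn. Selective loss is possible, not established.
- *A patient who takes anti-inflammatories for pain, or comes late, would be removed.* Section 6.3 asks that anti-inflammatories be avoided unless strictly necessary and that any use be recorded, so they are not prohibited. No visit windows are defined.
- *The unblinded doctor decides on removal.* No section says who decides. The injecting doctor is simply not excluded, and 11.5 describes masking of the researcher as left for later.
- *A shift of so many VAS points can be stated.* The documents give no outcome gap between removed and retained patients.

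The reply is also right that editing 5.6 alone would leave major violators outside the efficacy set in 11.3.2. On safety, patients withdrawn for an adverse event stay in the safety analysis, and the safety population in 11.3.3 includes all treated patients. That population keeps the patient in the denominator, but it does not supply visits that were not held.

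**Conclusion.** The point holds as a gap in data collection. After the injection, items 3, 5 and 6 can end a treated patient's participation. Section 5.8 preserves protocol follow-up only for adverse-event patients, and its check-ups cover one arm and omit most efficacy measures. V2–V5 efficacy and safety data can therefore be lost, possibly in relation to outcome or arm.

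The size is unknown. Each removal is 8.3% of an arm. Random loss would cost only precision, whereas the upper-bound case of worst-first loss in one arm would raise the type I error to 0.075 with one patient removed and 0.166 with three. This rests on reading the 5.8 expectation as referring to adverse-event patients, which is its grammatical antecedent in an imperfect text. It is a cheap improvement, not a flaw that invalidates the trial. The mismatch on the end of adverse-event follow-up is a separate and minor contradiction.

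**What to change.** - **Section 5.6.** State that after V1 a protocol deviation is recorded and does not by itself end follow-up. Treated patients in both arms who meet items 1, 3, 5 or 6 are asked to keep the scheduled V2–V5 assessments unless they withdraw consent, die or are lost to follow-up. The investigator remains free to omit an assessment for the patient's safety.
- **Section 11.3.2.** Add an efficacy analysis of all treated patients as randomised beside the per-protocol set. Without it, the collected data of major violators would not enter any efficacy analysis.
- **Sections 5.6 and 5.8.** Reconcile the two statements on when adverse-event follow-up of withdrawn patients ends.

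The cost is mainly wording, made as a written amendment under 9.2 with approval where required, plus one further analysis. The visits are already planned for every patient, so no new procedure is added. The downside is a few more completed visits in patients with deviations.

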5.8 FOLLOW-UP OF PATIENTS

The research team will inform all patients entering the study of the need to follow a specific periodic control and the importance of going to the planned visits.

To patients who experience adverse events (regardless of whether they have dropped out or withdrawn from the study) will be followed until the incidence has subsided. resolved or stabilized at a level acceptable to both the coordinator and the promoter of the study. As it is a single administration, the option of withdrawal of the medication so it is expected that these patients can continue the follow-up provided in the protocol. All patients included in the study who received cell therapy (including patients who have voluntarily left the study or are withdrawn from it) will continue regular check-ups after participation in the study. These controls will be carried out in the Orthopedic Surgery and Traumatology Service of the Hospital Clínico Universitario de Valladolid with a frequency not less than once a year. These controls should include a clinical evaluation, an X-ray and a general analysis (acceptable if they have been carried out up to 3 months before the visit). The follow-up will be done with a minimum of 5 years. In case that any relevant information was detected for the study related to both the efficacy of the product as well as the safety of the subject (and attributable to the therapy received) is will notify the promoter, initially by telephone and, if deemed appropriate, facilitating supporting documentation (signed report or adverse event form serious) by fax or email.

In addition, and as indicated in the next point, to all patients who have received medication in the study will be given a Participation Card. At this time The research team will ask them that, in case of presenting a health problem relevant inform the doctor who attends you about your participation in said trial clinician by presenting said card. Particular attention will be paid to possibility of histological study if at any time a surgical technique is practiced on the treated area. This follow-up is not required for control patients.

5.9. STUDY PARTICIPATION CARD

All patients who have received the study medication will be given a identification tracking card so that, if necessary, you can contact the research team. This card will have a DNI size so that it can always be carried in the patient's portfolio and will contain the following text:

IDENTIFICATION ČARD:

The holder of this card, Mr / Mrs:	is participating
or you have participated in a clinication	al trial of cell therapy in which you received treatment
with allogeneic mesenchymal cells	(Protocol code: Disc_allo_MSV). Saying treatment
was administered on the day:	and corresponds to the number of
Serie If you or your do	ctor need additional information about the study or
the treatment, or report an incident	, please contact:
Principal investigator:	•

Principal investigator:

relephone contact.	
Service:	

Center:

If it is not possible to contact the Principal Investigator, please contact with the Spanish Agency for Medicines and Health Products ([name]. [contact])

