6. TREATMENT AND STUDY PROCEDURES

6.1 IMP AND REFERENCE THERAPY

The product or drug under study is, in the control arm, the usual treatment based on of rehabilitation physiotherapy, postural hygiene and pharmacotherapy together with the injection of 2 ml 1% mepivacaine (obtained by mixing 1 ml of 2% mepivacaine with 1 ml of serum physiological saline) in the area of the paravertebral muscles close to the affected segment, using the same maneuvers as in the intervention in the experimental arm. (see section 2.4). In the experimental arm, the investigational drug or product is MSV, which are bone marrow mesenchymal cells processed according to the IBGM system from Valladolid, suspended in isotonic Ringer-lactate medium with human albumin at 0.5% and 5 mM glucose. Cell dose: $25x106 \pm 5x106$ MSV, in a volume of 2 ml of cell suspension. Stability demonstrated is> 12 hours at 4-20 °C. The whole process of obtaining MSV is carried out by highly qualified specialists in crops cell phones and is developed in the Cell Production Unit of Citospin (Parque Científico de

la UVa), meeting GMP criteria and following protocols approved by the AEMPS (PEI No. 10-134).

In the validations carried out, MSV has been shown to possess the characteristics typical MSC defined by the Society for Cellular Therapy (Dominici et al., 2006): 1) Adherence to plastic in cultivation; 2) Expression of CD73, CD90 and CD105 antigens. 3) Absence of hematopoietic antigens, markers of monocytes, macrophages and B lymphocytes.

4) In vitro differentiation capacity in osteoblasts, adipocytes and chondrocytes. Watch details in Figures 2 and 3.

6.1.1. Obtaining, cultivating and expanding MSV.

The processing and multiplication of harvested bone marrow cells using the IBGM procedure will last 3-4 weeks. The responsible medical team is expert in the management of the selection, culture and collection procedure of the cell product that, in its status available for application, is called MSV (the V added to the initials usual ones comes from Valladolid, to indicate that it follows the procedure developed, validated and authorized in our Cell Production Unit)).

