6.5. MANAGEMENT OF STUDY MEDICATION

The study medication, properly packaged MSV in a thermostatic container, was transported immediately after production to the application center. Has a stability longer than 12 hours at room temperature and is given as an injection in the area of the nucleus pulposus of the affected spinal segment.

7. DEVELOPMENT OF THE TEST AND ASSESSMENT OF THE RESPONSE 7.1 ASSESSMENT OF THE RESPONSE

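### The only participation-card text in section 5.9 says its holder received allogeneic cells; because neither recipients nor timing are fixed, it could reveal the arm to masked patients or be false for controls

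*Combined protocol and SAP*

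**What the plan says.** Section 5.9 defines who gets the card: "All patients who have received the study medication will be given a identification tracking card". It then fixes the wording. The holder is, or has been, in a "trial of cell therapy in which you received treatment" with allogeneic mesenchymal cells, followed by spaces for the treatment date and series number. The card names the principal investigator as the contact, with a fallback: "If it is not possible to contact the Principal Investigator, please contact with the Spanish Agency for Medicines and Health Products".

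Section 5.8 introduces the card in slightly different terms: "to all patients who have received medication in the study will be given a Participation Card". This comes straight after the long-term check-ups, where the group is narrower: "All patients included in the study who received cell therapy" "will continue regular check-ups after participation in the study", with some text between these two phrases. Section 5.8 closes by exempting control patients from the follow-up just described.

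Sections 1 and 4.1 state that the patient is masked, and section 4.2 says that randomization is blind to the patient. The VAS, Oswestry and SF-12 questionnaires are completed at 3, 6 and 12 months (sections 7.2.1 and 11.2.1). The visit schedule in section 7.2 does not mention the card.

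**The concern.** A card that names the experimental product, given to a patient who is still completing questionnaires, undoes the masking for that patient. The three patient-rated scales are the outcomes most open to expectation. Section 11.5 expects placebo improvement of up to 30% and relies on the control arm to discount it, which works only if expectation is alike in both arms. The same section describes patient-level blinding as feasible, so it is the one layer of masking that the protocol nowhere gives up.

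If the card instead goes to everyone, it misinforms. Its purpose is to tell a treating doctor what the holder received, and for a control it would name the wrong treatment.

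**Working it through.** The protocol gives no figure for this point, so the check is a comparison of sections and a head count from 12 patients per arm, 24 in total (sections 5.4 and 5.7).

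**Who receives the card?**

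- *Cell-treated patients only.* Section 6.5 uses the term for the cells: "The study medication, properly packaged MSV in a thermostatic container". The matching heading in Annex I does the same. The card's cell wording and series number fit only this group, since section 6.4 registers the cell product per patient. The control exemption at the end of section 5.8 may also extend to the card, though its scope is unclear.
- *Both arms.* Section 5.8 gives the card to those who had medication in the study, after using the narrower cell-therapy group for the check-ups. Section 6.1 opens with "The product or drug under study is, in the control arm, the usual treatment", so it counts the control as a product under study. The general instructions in Annex IV treat the control as an investigational medicine, although only for the adverse-reaction form.

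Neither reading is excluded.

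**When is it issued?** The card wording covers a holder who is still in the trial and one who has finished, so it allows issue before V5. Its placement in section 5.8, after the post-study check-ups, also allows issue after V5. No date is given.

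**Consequences of each combination**

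| Recipients | Issued before V5 | Issued after V5 |
|---|---|---|
| MSV patients only | Text tells up to 12 of 24 (12/24 = 50%) their arm; the other 12 could infer theirs only if they know that such cards exist | That patient's own ratings are not affected |
| Both arms | Text is false for up to 12 of 24; the shared statement does not separate the arms, but it tells every holder that cells were given | Text is still false for up to 12 of 24 |

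Under the both-arms reading, section 5.9 also does not say what a control's card would show as series number.

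Only one of the four combinations, MSV patients after V5, is free of both problems. No section reviewed states it.

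**The case against.** The strongest reply is that the harmful combination is not established. Bias needs issue to MSV patients only and also before V5, and no sentence says both. The order of section 5.8 makes late issue a natural reading. For a control to learn anything from having no card, he would have to know that cards exist. Annex II, which might show this or contain a timing rule, was not in the copy reviewed. The English is a rough translation, so fine contrasts between terms carry little weight. The main goal in section 3.1 is feasibility and safety, and the card does not touch imaging.

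Most of this stands, and it limits the claim. It does not remove it: a prescribed text that is harmless under only one unstated combination conflicts with stated masking or with fact under the others.

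Three stronger readings are tempting, and the documents do not support them:

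- A reader might infer that the trial will be unblinded. The documents show only that nothing reviewed prevents it.
- A reader might infer that both arms are meant, so that 12 false cards are planned. The wording for that is thin, and section 6.5, Annex I and the control exemption in section 5.8 point the other way.
- A reader might put a false-positive rate on the bias. Any such rate would rest wholly on an assumed difference in expectation between the arms, for which the protocol gives no basis.

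**Conclusion.** The point holds in conditional form. Section 5.9 prescribes one text naming the cell treatment, and sections 5.8 and 5.9 leave recipients and timing open. Depending on how they are read, the card tells up to 12 of 24 patients their arm while they are still rating their own outcomes, is false for up to 12 controls, or leaves the ratings unaffected. The size of any bias in VAS, Oswestry or SF-12 cannot be derived from the documents. The conclusion assumes that the missing Annex II contains no neutral card and no timing rule.

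A separate matter should be judged on its own. Sections 1 and 4.1 call the trial double blind, while section 11.5 leaves masking of the researcher and of the analysis for later. Those sections must be reconciled, but this adds nothing to the weight of the card issue.

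**What to change.** In sections 5.8 and 5.9:

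- Give every treated patient in both arms the same neutral card until the follow-up needed for the blinded comparison is complete. It would say that the holder took part in Disc_allo_MSV and received either allogeneic MSV or a control injection.
- Keep the contact route already on the card, and state that a treating doctor can obtain the allocation through it.
- Issue a card naming the cell treatment and series number only afterwards, and only to MSV recipients.
- Say explicitly who receives each card and when, and use one term for the recipients in both sections.

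The cost is one neutral text, edits to two sections and one re-issue for up to 12 MSV patients. The downside is that a treating doctor must call to learn the allocation until the specific card is issued. If the release point is the last patient's V5, and recruitment keeps to the 6-month maximum in section 1, the earliest patients would wait up to about 6 months beyond their own V5. This assumes a similar interval from inclusion to treatment for all patients.
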